The main purpose of this amendment is to address concerns raised during review of the study protocol by regulatory authorities (BfArM) regarding inclusion/exclusion criteria and the conditions requiring temporary interruption or permanent discontinuation of study treatments. The following changes to the protocol have been made in light of these requests:

- Inclusion criterion 3 was modified to clarify that the study will enroll patients scheduled for cataract surgery (not yet performed) (*Section 5.1*). The criterion has been split into two, one indicating the inclusion of patients scheduled for surgery (not yet performed), and the other stating that only patients who completed surgery without complications will be randomized.
- Exclusion criterion 9, which previously referred to contraindications to ocular treatment with levofloxacin, tobramycin or dexamethasone in general terms, now indicates all the specific contraindications to study treatments as stated in their respective Summary of Product Characteristics (SPC) or Investigator's Brochure (IB) (*Section 5.2*). Since the warnings and precautions related to study treatments apply to situations that may arise following screening, a sub-section has been added to the treatment section of the protocol listing all the warnings and precautions as per SPC or IB (*Section 6.6*). Specific situations requiring study treatment discontinuation according to SPC or IB have been added to *Section 7.1*.
- Exclusion Criterion 11 now states that participation in previous clinical studies is possible if at least 5 half-lives of the IMP used in the previous studies have passed between the end of treatment in the previous study and the start of treatment in this clinical study.
- The amendment now states that temporary interruption of study treatment and dose modifications are not foreseen in the protocol (*Section 7.1*). Additional information has also been added indicating the conditions for permanent discontinuation.

The amended protocol also clarifies that testing of visual acuity is to be performed according to local practice. Minimum visual acuity of the contralateral eye required for study entry (Exclusion criteria 8) has consequently been converted and is now stated using various standards (*Section* 5.2).

Changes to specific sections of the protocol are shown in the track changes version of the protocol using strike through red font for deletions and red underline for insertions.

STATEMENT OF COMPLIANCE

12 July 2018

Version 2.0

The trial will be conducted in accordance with International Conference on Harmonization Good Clinical Practice (ICH GCP) and all applicable laws and regulations. The Principal Investigator will assure that no deviation from, or changes to the protocol will take place without prior agreement from the Sponsor and documented approval from the Institutional Review Board (IRB) or Independent Ethics Committee (IEC) and/or Competent Authority, except where necessary to eliminate an immediate hazard to the trial participants. All personnel involved in the conduct of this study have completed ICH GCP Training.

The protocol, informed consent form(s), recruitment materials, and all participant materials will be submitted to the IRB/IEC for review and approval. Approval of both the protocol and the consent form must be obtained before any participant is enrolled. Any amendment to the protocol will require review and approval by the IEC before the changes are implemented. All changes to the consent form will be IEC approved; a determination will be made regarding whether a new consent needs to be obtained from participants who provided consent, using a previously approved consent form.

PROTOCOL SUMMARY

1.1 SYNOPSIS

Protocol Number	LevoDesa_04-2017
EudraCT Number	2018-000286-36
Title	An international, multicenter, randomized, blinded-assessor, parallel-group clinical study comparing eye drops of combined LEvofloxAcin + DExamethasone foR 7 days followed by dexamethasone alone for an additional 7 days vs. tobramycin + dexamethasone for 14 days for the prevention and treatment of inflammation and prevention of infection associated with cataract surgery in adults – LEADER 7.
Phase	111
Sponsor	NTC S.r.l.
International Chairman	[name], Full Professor of Ophthalmology, Director of Clinica Oculistica of the Università Vita-Salute, Istituto Scientifico San Raffaele, Milan.
Investigational sites	The study will be conducted at approximately 80 centers located in Italy, Germany, Spain and Russia.
Rationale	In clinical practice, topical treatment following cataract surgery is frequently administered using a combination between an antibiotic and a corticosteroid to promote patient adherence to therapy and to obtain both prevention of infection and treatment of post-surgical inflammation. The combination of tobramycin and dexamethasone is among the most widely used combinations, but treatment usually lasts for two or more weeks, sometimes tapering posology over several weeks afterwards. This therapeutic strategy may however be inappropriate in terms of preventing the development of bacterial resistance, which is favored by prolonged treatment and the use of sub-therapeutic doses. For this reason, antibiotic treatment should not be prolonged beyond the time necessary for the healing of surgically induced epithelial lesions, and therefore should not last more than a week.
	Based on these considerations, a product associating a broad-spectrum antibiotic with a highly effective corticosteroid that can be used for a short period of time (one week) would be of considerable interest.
	The combination of levofloxacin 0.5% and dexamethasone 0.1% tested in this study is the first combination of a steroid and a quinolone under development and represents a major step forward in this direction.
	The purpose of this study is to evaluate the efficacy of a combination of levofloxacin and dexamethasone by demonstrating that its use for a limited time of one week, followed by treatment with dexamethasone alone, is not inferior to longer treatment with tobramycin + dexamethasone in

	preventing and treating ocular inflammation and in preventing post- operative infection while limiting the emergence of antibiotic resistance.					
Objectives	Efficacy : to demonstrate the non-inferiority of combined levofloxacin + dexamethasone eye drops for 7 days followed by dexamethasone eye drops alone for an additional 7 days vs. standard treatment tobramycin + dexamethasone eye drops for 14 days in the prevention and treatment of postoperative ocular inflammation and prevention of infection.					
	 Safety and tolerability: To evaluate the safety of combined levofloxacin + dexamethasone eye drops. To evaluate the tolerability of combined levofloxacin + dexamethasone eye drops. 					
	Compliance : to evaluate compliance with prescribed treatment.					
Endpoints	 Primary efficacy The proportion of patients without signs of anterior ocular chamber inflammation (sum of cells and flare score = 0) after 14 days of treatment. Secondary efficacy Incidence of endophthalmitis Proportion of patients without signs of anterior ocular chamber inflammation after 3 and 7 days of treatment Conjunctival hyperemia after 3, 7 and 14 days of treatment Total Ocular Symptoms Score (TOSS) after 3, 7 and 14 days of treatment Ocular pain/discomfort after 3, 7 and 14 days of treatment Use of rescue therapy during treatment Safety Intraocular pressure (IOP) Visual acuity Adverse events Tolerability Global evaluation Burning, stinging, blurred vision Compliance Assessment of patient diary 					
Type of study	This is an international, multicenter, randomized, blinded-assessor, parallel- group clinical study. The Investigators in charge of evaluating study parameters will be blinded to treatment assignment. A separate investigational staff will be unblinded and responsible for assigning and dispensing/return study products.					
Study Population	The study will enroll 800 adult male and female patients undergoing cataract surgery.					
Inclusion criteria	Inclusion criteria prior to surgery					

	 Signed written informed consent must be obtained before any assessment is performed Male or female, age ≥40 years Scheduled senile or presenile cataract surgery (not yet performed). Willing to interrupt the use of contact lenses for the entire duration of
	 Able and willing to follow study procedures For females of childbearing potential, the use of highly effective contraception and agreement to use such a method during study participation Inclusion criteria following surgery
Exclusion criteria	 Surgery completed without complications Ocular conditions that at the discretion of the Investigator may interfere with the efficacy and/or safety evaluations (e.g. ocular herpes, blepharitis, conjunctivitis, uveitis, keratitis, diabetic retinopathy, retinal vein occlusions, retinal vasculitis, retinal angiomatous proliferation, pseudoexfoliation syndrome, intraoperative floppy iris syndrome, etc.) Patients undergoing bilateral cataract surgery Patients under treatment with prostaglandin analogues or intravitreal injections of anti-VEGF (vascular endothelial growth factor) drugs Systemic diseases that may interfere with the results of the study (e.g. rheumatoid arthritis, Sjögren's syndrome, Behçet's disease, systemic lupus erythematosus, scleroderma with major ocular involvement, etc.) Any condition that could interfere with correct instillation of eye drops Ocular surgery in the study eye (including laser surgery) in the 3 months before screening Monocular patients Visual Acuity (VA) < 20/80 of the contralateral eye measured as ETDRS or Snellen 20 feet, equal to 0.25 in decimal Contraindication to ocular treatment with Tobradex®, Maxidex® or levofloxacin/dexamethasone as follows: Herpes simplex keratitis, vaccinia, varicella and other viral diseases of the cornea and conjunctiva Fungal and mycobacterial diseases of ocular structures or untreated parasitic eye infections Uncontrolled intraocular hypertension Uncontrolled glaucoma Tobradex[®] is contraindicated also in case of untreated purulent infections of the eye, whereas Maxidex[®] is contraindicated in acute, untreated bacterial infections.
	 Hypersensitivity to the products or their excipients Participation in other clinical studies if at least 5 half-lives of the IMP used in the previous studies have not passed between the end of treatment in the previous study and the start of treatment in this clinical study.

	12. Pregnancy or breastfeeding
Study drugs	Test arm : levofloxacin + dexamethasone ophthalmic solution containing levofloxacin hemihydrate 5.12 mg/ml, corresponding to 5 mg/ml levofloxacin + dexamethasone 21-phosphate 1.32 mg/ml, corresponding to dexamethasone 1 mg/ml for 7 days, 1 drop - 4 times a day, followed by dexamethasone ophthalmic suspension 1.0 mg/ml (Maxidex [®]) for an additional 7 days, 1 drop - 4 times a day. Control arm : tobramycin + dexamethasone ophthalmic suspension containing tobramycin 3 mg/ml + dexamethasone 1 mg/ml (Tobradex [®]) for 14 days, 1 drop - 4 times a day.
Study procedures	 Patients scheduled for cataract surgery who have provided written informed consent will undergo screening procedures to verify eligibility. Immediately following phacoemulsification performed by an experienced surgeon, patients who complete surgery without complications will be assigned to one of the following two treatment groups in a 1:1 ratio according to a randomization list stratified by center: Study arm: levofloxacin + dexamethasone eye drops for 7 days followed by dexamethasone eye drops (Maxidex[®]) for another 7 days. Control arm: tobramycin + dexamethasone eye drops (Tobradex[®]) for 14 days. Treatment will begin either immediately after randomization according to local routine clinical practice (in those patients who are not bandaged after surgery), or immediately after removal of dressing of operated eye. Doses administered on the same day as surgery will be considered additional to the full protocol dosage regimen (4 instillations per day for 14 days). Patients will be given a diary on which to record times of instillation. Diaries will be collected to evaluate compliance with treatment. After surgery, patients will undergo visits on Day 4, Day 8 and Day 15 (end of study) to evaluate efficacy, safety and tolerability.
Sample size	The study plans to enroll 800 patients: 400 patients will be assigned to the test treatment and 400 to standard treatment. A sample size of 362 patients in each group is required to assess the non-inferiority of the test treatment vs. the standard therapy (i.e. lower limit of the 95% Confidence Interval of the difference in proportions, $\pi T - \pi S > -0.10$) with 80% power and by applying a two-group large-sample normal approximation test of proportions with a one-sided 0.025 significance level, assuming that the expected difference in proportions is 0 and the proportion in the standard group is 0.64. The total sample size (362 + 362 = 724) is adjusted to 800 patients considering an expected dropout rate of about 10% using Freedman's formula: n'= 100*n/100-x, where x is the expected dropout rate.
Statistics	Primary endpoint : The proportion of patients without signs of anterior chamber inflammation (sum of cells and flare score = 0) after 14 days of treatment will be calculated to evaluate the non-inferiority of the test treatment vs. the standard therapy. Non-inferiority will be assessed by computing the two-tailed 95% confidence interval (CI) of the difference

	between the two proportions $\pi_T - \pi_S$. Non-inferiority is met if the 95% CI does not cross the predefined non-inferiority margin $\Delta = -0.10$ and lies entirely to the right of the margin (i.e. non-inferiority will be demonstrated if the lower bound of the two-sided 95% CI of the difference is > -0.10). If the 95% CI of the difference lies completely to the right of 0, the test treatment can be considered more effective than the standard treatment at a 5% significance level. Secondary endpoints : Descriptive statistics and two-sided 95% CIs of the difference between treatments will be computed for the secondary endpoints.
Duration of the study	Estimated date of the first visit of the first patient (FPFV): Q3, 2018
	Estimated date of the first visit of the last patient (LPFV): Q1, 2019
	Estimated date of the last visit of the last patient (LPLV): Q1, 2019
Participant Duration	The study, for each patient, will last 14 days following cataract surgery.
Version and Date	V 2.0 – 12 July 2018

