8 STUDY ASSESSMENTS AND PROCEDURES

8.1 SCHEDULE OF ASSESSMENTS

The following visits will be performed as listed in the SoA. Additional visits will be made available to patients in case of need.

Visit 1: Screening (to be performed not more than 28 days prior to surgery)

Upon signing the informed consent form each patient is uniquely identified by a patient ID number which is composed of the site number and a sequential number assigned automatically by the eCRF. Once assigned to a patient, the patient ID number will not be reused.

At screening, after obtaining signed written informed consent, inclusion/exclusion criteria will be checked and the following assessments will be performed/data collected:

- Demographics
- Medical history
- Use of concomitant medications

- Slit lamp examination
- Intraocular pressure
- Visual acuity
- Adverse events

Visit 2 - Day of surgery

Prior to surgery, inclusion/exclusion criteria will be rechecked, and the following assessments will be performed/data collected:

- Use of concomitant medications, including prophylactic pre-operative medications to be stopped before surgery
- Adverse events occurred after previous visit.

Women of childbearing potential will be required to undergo a urine pregnancy test (dipstick).

Patients who completed surgery without complications will be randomized to one of the two treatment arms and will be provided with study drug needed until visit at day 8 (first period of treatment) and a diary on which to record times of instillations.

Visit 3 - Visit on day 4 after 3 full days of treatment

On Day 4, patients should return their diaries to evaluate compliance. The following assessments will be performed/data collected on Day 4:

- Concomitant medications
- Slit lamp examination
- Evaluation of any ocular infections
- Total Ocular Symptom Score (TOSS)
- Ocular pain/discomfort
- Use of rescue therapy
- Intraocular pressure
- Local tolerability (global evaluation/burning, stinging, blurred vision)
- Adverse events occurred after previous visit

Visit 4 - Visit on day 8 after 7 full days of treatment

On Day 8, patients should return unused medication and completed diary to evaluate compliance and will receive a new supply of medication needed until end of study and a new diary. The second period of treatment will start after the new supply.

The following assessments will be performed/data collected on Day 8:

• Concomitant medications

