8.2 EFFICACY ASSESSMENTS

• Slit lamp examination

A slit lamp examination will be performed at Visit 1 (screening) and on Day 4 (Visit 3), Day 8 (Visit 4), and Day 15 (Visit 5) to evaluate cells in the anterior chamber and aqueous flare as follows:

Cells in anterior chamber: results are to be provided as a score: 0 = no cells; 1 = 1-5 cells; 2 = 6-15 cells; 3 = 16-30 cells; 4 = >30 cells.⁴⁸

Aqueous flare (Tyndall effect): results are to be provided as a score: 0 = absent; 1 = trace barely detectable; 2 = mild intensity (iris and lens details clear); 3 = moderate intensity (iris and lens details not clear); 4 = strong intensity (iris and lens details not visible and fibrin in the anterior chamber).⁴⁴

Conjunctival hyperemia will be evaluated and results provided as a score as follows: 0 = absence of inflammation, 1 = mild inflammation (some vessels injected), 2 = moderate inflammation (diffuse injection of vessels, but individual vessels are still discernable) 3 = severe inflammation (intense injection of vessels, individual vessels not easily discernable).⁴⁵

• Endophthalmitis

All cases of endophthalmitis occurring following cataract surgery are to be reported at all visits.

• Total Ocular Symptom Score (TOSS)

The TOSS is a patient-reported evaluation of 3 ocular symptoms: itching/burning, hyperemia of conjunctiva and tearing. Each symptom is given a score: 0 = none, 1 = mild, 2 = moderate, 3 = severe. The TOSS will be evaluated on Days 4, 8, and $15.^{46}$ See Appendix 1.

• Ocular pain/discomfort

Overall ocular pain and discomfort will be evaluated by the subject at Days 4, 8 and 15 on a 4-point scale (0 = absent, 1 = mild, 2 = moderate, 3 = severe).

• Use of rescue therapy

All rescue therapy used following cataract surgery is to be reported at all visits (see *Section 6.5.2*).

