9.4.3 ANALYSIS OF THE SECONDARY ENDPOINT(S)

Descriptive statistics and two-sided 95% CIs of the difference between treatments will be computed for the following secondary endpoints:

- Incidence of endophthalmitis
- Proportion of patients without signs of anterior chamber inflammation (sum of cells and flare score = 0) after 3 and 7 days of treatment
- Proportion of patients with conjunctival hyperemia score equal to 0 after 3, 7 and 14 days of treatment
- Proportion of patients with TOSS score equal to 0 after 3, 7 e 14 days of treatment
- Proportion of patients with ocular pain/discomfort score equal to 0 after 3, 7 and 14 days of treatment
- Proportion of patients using rescue therapy during treatment

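### TOSS and ocular pain/discomfort have no pre-operative score, so their between-arm differences cannot be adjusted for a patient-reported baseline; the cost is nil to modest precision on descriptive secondary endpoints

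*Combined protocol and SAP*

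**What the plan says.** The secondary efficacy endpoints in the synopsis (1.1) include "Total Ocular Symptoms Score (TOSS) after 3, 7 and 14 days of treatment". Section 8.2 fixes the timing of both patient-reported endpoints. For TOSS: "The TOSS will be evaluated on Days 4, 8, and" 15. For pain: "Overall ocular pain and discomfort will be evaluated by the subject at Days 4, 8 and 15". The schedule of activities in 1.3 and the visit lists in 8.1 agree. The first of these visits is headed "Visit 3 - Visit on day 4 after 3 full days of treatment".

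The screening list in 8.1 opens "At screening, after obtaining signed written informed consent, inclusion/exclusion criteria will be checked and the following assessments will be performed/data collected". It then names demographics, medical history, concomitant medications, slit lamp, intraocular pressure, visual acuity and adverse events. Neither symptom score appears there, nor in the list for the day of surgery.

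Section 9.4.3 turns both scores into a yes/no outcome: "Proportion of patients with TOSS score equal to 0 after 3, 7 e 14 days of treatment" and "Proportion of patients with ocular pain/discomfort score equal to 0 after 3, 7 and 14 days of treatment". That makes six comparisons (two endpoints at three visits). The method is "Descriptive statistics and two-sided 95% CIs of the difference between treatments will be computed for the following secondary endpoints", with no covariate named. Section 9.1 sets no formal hypotheses for the secondary endpoints.

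The form in Appendix 1 asks about itching/burning, redness and tearing. It gives no recall period and does not mention the operation or the operated eye.

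**The concern.** A patient who already had itching, redness or tearing before surgery cannot be told apart, in the data, from one whose symptoms come from the operation or the drops. Both score above 0 and both count as not having reached the endpoint. Because the pre-operative score is never taken, no later analysis plan can bring it in.

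Precision is at stake. Patients with and without earlier symptoms may have quite different chances of scoring 0. When they are mixed without a baseline term, that difference goes into the variance of the between-arm comparison. If one arm happens to receive more of these patients, the observed difference moves and cannot be corrected with a patient-reported baseline.

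The plan already has such a value for a related endpoint: conjunctival hyperemia is part of the slit-lamp examination, which is done at screening. Section 9.4.1 also counts efficacy data among the baseline features, and for TOSS and pain there will be none.

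**Working it through.** **The plan's own figure.** The documents give no sample size, power or expected rate for TOSS or pain. The only sizing is for the primary endpoint (9.2), and it reproduces: n = 2 × 0.64 × 0.36 × (1.960 + 0.842)² / 0.10² = 361.7, so 362 per group. The present point does not touch it.

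**Inputs.** From the documents: 400 per arm (9.2), 1:1 allocation, and an endpoint of score 0. Assumed, because the documents are silent:
- share with pre-operative symptoms, q = 0.2 to 0.4;
- Day 15 proportion with TOSS = 0 among patients without them, a = 0.6 to 0.7;
- the same proportion among patients with them, b = 0.2 to 0.4.

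**Formulas.**
- Overall rate: m = (1 − q)a + qb.
- Unadjusted variance per patient: m(1 − m).
- Variance within baseline strata: (1 − q)a(1 − a) + qb(1 − b).
- The gap between the two: q(1 − q)(a − b)².
- 95% half-width of the difference: 1.96 × √(2 × variance / 400).
- One-SD shift in the difference from chance imbalance: √(2q(1 − q)/400) × (a − b).

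| | Weak end | Middle | Strong end |
|---|---|---|---|
| q, a, b | 0.2, 0.6, 0.4 | 0.3, 0.7, 0.2 | 0.4, 0.7, 0.2 |
| m | 0.56 | 0.55 | 0.50 |
| Unadjusted variance | 0.2464 | 0.2475 | 0.2500 |
| Within-stratum variance | 0.2400 | 0.1950 | 0.1900 |
| Gap | 0.0064 | 0.0525 | 0.0600 |
| Variance reduction | 2.6% | 21% | 24% |
| Half-width, unadjusted (points) | 6.88 | 6.89 | 6.93 |
| Half-width, adjusted (points) | 6.79 | 6.12 | 6.04 |
| Imbalance, 1 SD (points) | 0.57 | 1.62 | 1.73 |

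The gain equals that from about 3% more patients at the weak end (1/0.974) and 32% more at the strong end (1/0.76). If a = b, the gap is 0 and the gain is nil. With fewer evaluable patients all half-widths grow, but the percentage reductions do not change.

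**Imbalance is not a second cost.** The imbalance SD is √(2 × gap / 400). In the middle column, √(2 × 0.0525 / 400) = 1.62 points. It is the same variance that the baseline term removes, and the planned unadjusted interval already contains it.

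**What adjustment does not change.** Suppose 20% never reach 0 whatever the treatment, and the arms truly differ by 10 points among the rest. The overall difference is 0.8 × 10 = 8 points. Standardising over the Visit 1 score gives 0.8 × 10 + 0.2 × 0 = 8 points again. The interval narrows, but the quantity estimated stays the same.

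**The case against.** The case for leaving the plan alone has several parts.

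- **No decision depends on these endpoints.** They are descriptive, and the primary analysis is unaffected. This stands and sets the weight of the point.
- **Eligibility limits the problem.** Exclusion 1 in 5.2 is open-ended and covers any ocular condition the investigator thinks may interfere; its examples include blepharitis, conjunctivitis and keratitis. Exclusion 4 names Sjögren's syndrome. Contact-lens wearers must stop wearing lenses for the study (5.1.1). These rules lower the share with long-standing symptoms by an unknown amount. They are partly discretionary and do not name dry eye, and without a Visit 1 score the remaining share cannot be shown.
- **Proxies exist.** Screening hyperemia relates to the redness item, and medical history may record chronic complaints. It would be too strong to say that nothing can be adjusted for. Neither replaces a patient's own rating of itching/burning, tearing or pain, and no adjusted analysis is planned.
- **Prediction is unproven.** Visit 1 may be up to 28 days before surgery, and section 2.2 links post-operative discomfort to the operation. The gain could be nil, most plausibly for pain, for which no rate or association is available.

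A reader might also infer three stronger things that the documents do not support:

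- that the comparisons are biased or the intervals invalid: allocation is randomised 1:1, so neither follows;
- that chance imbalance is a harm on top of the wider interval: it is the same variance;
- that adjustment would stop long-standing symptoms counting as failures or undo dilution: with a score of 0 still required, it would do neither.

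**Conclusion.** The point holds as a small, optional improvement. It is certain from 1.3, 8.1, 8.2 and 9.4.3 that no pre-operative TOSS or pain/discomfort score exists and that both are compared as unadjusted proportions at 0. What follows is a possible loss of precision. For Day 15 TOSS, a baseline term would cut the variance by about 3% to 24%, taking the half-width from 6.9 to 6.8 points at the weak end and from 6.9 to 6.0 at the strong end.

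That range rests wholly on assumed rates and on 400 patients per arm. It falls to nil if pre-operative symptoms do not predict later ones. Days 4 and 8, and pain at any visit, are not quantified. The planned intervals remain valid, and neither the primary endpoint nor its sample size is affected.

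**What to change.** 1. In 1.3, 8.1 and 8.2, add the three TOSS items and the single pain/discomfort item for the study eye at Visit 1. Appendix 1 names no eye, so the same instruction should apply at the later visits.
2. In 9.4.3, keep the unadjusted differences as planned. Beside them, give a risk difference with 95% CI standardised for the Visit 1 score of the same endpoint (0 versus above 0).
3. Adjustment improves precision only. To show how far long-standing symptoms keep patients from reaching 0, also tabulate both endpoints descriptively by arm among patients who scored 0 at Visit 1.
4. State how patients without a Visit 1 score enter the adjusted analysis.

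The cost is four extra questions and one eCRF page at an existing visit, one covariate and one further table. Patients screened before the change would lack the score, so the gain would be smaller if many had already been screened.
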